13.2 Data Safety Monitoring Board (DSMB)

An independent DSMB, appointed by NIH and governed by NIH policy, will be charged with monitoring study-wide safety and clinical events on a regular basis (semi-annually). In particular, the DSMB will review the following SAE's and the following specific clinical and safety events: death, hospitalization, hospitalization/observation unit stay lasting less than 24 hours, emergency room visit, urgent clinic visits, and adverse events occurring while participant performing the REHAB-HF intervention (including angina, syncope/presyncope, palpitations, symptomatic hypoglycemia and/or falls), cardiovascular events (including worsening heart failure, acute coronary syndrome, arrhythmia, and stroke), nursing home placement, and injury (or fall) during rehabilitation.

The protocol will guard against "unreasonable harm" by performing interim looks at DSMB meetings. The events included in this analysis will be death, disabling stroke, myocardial infarction, resuscitated sudden cardiac death, sustained symptomatic ventricular tachycardia, and ED visit or hospitalization for serious fall / injury.

14. Statistical Considerations

14.1 Statistical Methods

The primary aim of the study is to assess the efficacy of the REHAB-HF intervention on physical function measured by the total SPPB score. The effect of the intervention on SPPB score measured 3 months post-randomization will be estimated and tested for significance using analysis of covariance, where the randomized arm is the between-subject grouping variable and the pre-randomized measure of SPPB score, clinical site, age, gender, and ejection fraction category (preserved vs. reduced) will be covariates. Least square means will be used to estimate the intervention effect. Tests will be conducted at the 5% two-sided level of significance.

The secondary aim of the study is to assess the intervention's effect on the total number of all-cause rehospitalizations during the 6 months following discharge from the index hospitalization. Since the count of all-cause rehospitalizations per participant may not be normally distributed, the effect of the intervention on total all-cause rehospitalizations will be estimated using a Poisson model for modeling count data, where the randomized arm is the between-subject grouping variable and clinical site, age, gender, and ejection fraction category will be covariates. A supplemental analysis will be performed adding the duration of the index hospitalization and the number of inpatient intervention sessions as additional covariates.

The proportion of the intervention's effect on total all-cause rehospitalizations that can be explained by its effect on 3-month SPPB score will be analyzed by multivariable regression between total number of all-cause rehospitalizations and the residual of the analysis of covariance model for 3-month SPPB omitting intervention from the model.

Similar statistical methods as described above will be used for all of the exploratory efficacy parameters.

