7.2.3 Initial Exercise Prescription

The initial rehabilitation exercise prescription will be individualized for each participant based upon functional performance level (1-4, from lowest to highest) in each domain using the objective criteria shown in Table 1. Performance level will be assessed in the first rehabilitation session in both the inpatient and outpatient setting. Using a standardized approach, exercises specifically targeted to the participant's functional level in each domain will be selected from the rehabilitation intervention protocols. We anticipate a range of initial performance levels based on the REHAB-HF pilot study where 40% of participants were initially at level 1 for most domains, 33% were at level 2, and 27% were at level 3.

Table 1. Performance Levels for Strength, Balance, Mobility and Endurance

	Level 1	Level 2	Level 3	Level 4	
Strength: Rise from chair	unable	at least once	5 times in > 15	5 times in ≤ 15	
without hand support	unable	at least office	but <60 sec.	sec.	
Balance: Standing	unable with feet	with feet together for	unsupported and	on 1 leg for 10	
	together for 10 sec.	10 sec.	reach forward 10 in.	sec.	
Endurance: Continuous	< 2 minutes	≥ 2 but < 10 minutes	≥ 10 but	≥ 20 minutes	
walking	< 2 minutes	2 2 but < 10 minutes	< 20 minutes	2 20 minutes	
Mobility: Gait speed	≤ 0.4 m/sec.	> 0.4 but ≤ 0.6 m/sec	> 0.6 but ≤ 0.8	> 0.8 m/sec.	
wobinty. Gait speed	≥ 0.4 m/sec.	> 0.4 but ≥ 0.0 III/Sec	m/sec.	/ 0.0 III/Sec.	

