14.2 Sample Size Justification

The REHAB-HF pilot study showed an estimated intervention effect of an increase of 1.13 units in 3-month SPPB score (the primary outcome) or a 17.9% relative increase above the least square mean for the attention control group, with a mean square error from the analysis of covariance model of 3.269. A clinically meaningful but small change in SPPB score is 0.5 units and a substantial change is 1.0 units.(159) This study is designed to have 80% power to detect a 10% treatment difference (0.63 absolute difference) in the 3-month least square mean of SPPB score. This requires 258 evaluable participants. In our pilot study, the observed retention rate was 89%. Conservatively assuming an 85% retention rate, the study requires randomizing 304 participants (25.3 per site per year).

In the completed pilot study, the number of all-cause rehospitalizations within 6 months was reduced 29.3% by the intervention (1.673 \pm 0.392 per patient in the attention control group vs. 1.157 \pm 0.349 in the intervention group). We performed additional work with an analysis of a contemporaneous sample of 239 consecutive patients aged \geq 65 years admitted with the primary diagnosis of ADHF. This confirmatory sample yielded a 6-month rehospitalization event rate estimate within 0.5% of our attention control group, giving confidence in our pilot study estimate. This study is designed to have 80% power to detect a 25% reduction (0.41 absolute difference) in the total number of all-cause rehospitalizations during the 6 months following the index hospitalization. This requires 334 evaluable participants. In the pilot study we were able to evaluate the number of hospitalizations within 6 months in 100% of participants.

Conservatively assuming up to 5% inevaluability, the study requires randomizing 352 total participants. Rounding up to 30 patients per site per yr, this study will randomize a total of 360 patients, providing > 80% power for the primary and secondary aims.

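### The only secondary outcome, total 6-month rehospitalizations, is tested with a Poisson model that makes no provision for over-dispersion, and the inputs behind its sample size need reconciling

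*Combined protocol and SAP*

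**What the plan says.** Section 12.2 names one secondary outcome, the number of rehospitalizations for any cause in the six months after index discharge. For its analysis, Section 14.1 states that "the effect of the intervention on total all-cause rehospitalizations will be estimated using a Poisson model for modeling count data", with randomized arm, clinical site, age, gender and ejection fraction category in the model. The reason given is that the counts may not be normally distributed; their variance is not discussed. The one supplemental analysis adds two covariates. The section closes by applying similar methods to the exploratory endpoints, which include other event counts (Section 12.3).

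The significance level appears in the paragraph on the primary aim: "Tests will be conducted at the 5% two-sided level of significance". I take it to apply to the secondary outcome too.

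Section 14.2 designs the trial for "80% power to detect a 25% reduction (0.41 absolute difference) in the total number of all-cause rehospitalizations" and continues: "This requires 334 evaluable participants". Allowing 5% inevaluability gives 352, rounded up to 360 randomized. The pilot is the stated basis: "the number of all-cause rehospitalizations within 6 months was reduced 29.3% by the intervention", with 1.673 ± 0.392 per control patient and 1.157 ± 0.349 per intervention patient. The section does not say what ± denotes, how many patients were in each pilot arm, or which variance and formula gave 334.

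**The concern.** Under a Poisson model the standard error of the rate ratio follows from the fitted mean alone. If patients differ in their underlying rehospitalization rates in ways that the covariates do not capture, the counts vary more than the model allows. The standard error is then too small, the test exceeds its stated level and the interval is too narrow.

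That is plausible here. Sections 3, 5 and 7.2.1 describe patients with many comorbidities, varied functional ability and high rates of frailty. Section 10.1.1 presents SPPB as a strong predictor of hospitalization, yet baseline SPPB is a covariate in the primary model and not in this one.

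At stake is a claim of fewer rehospitalizations, on the outcome that fixed the trial's size, made more easily than the stated 5% level permits.

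**Working it through.** **1. Pilot figures (Section 14.2).**
- 1 − 1.157/1.673 = 0.308, so the reduction is 30.8% against the 29.3% stated.
- 0.25 × 1.673 = 0.418, against the 0.41 stated.
- A control mean near 1.637 would fit both stated figures: 1 − 1.157/1.637 = 29.3% and 0.25 × 1.637 = 0.409. A transposed digit is therefore possible but cannot be confirmed. An adjusted estimate could also explain 29.3%.

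**2. Attempt to reproduce 334.** With two-sided 5%, 80% power and 1:1 allocation, k = (1.960 + 0.842)² = 7.849. For Poisson counts, n per arm = k(m₀ + m₁)/d², where m₁ = m₀ − d.

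| Control mean m₀ | Difference d | n per arm | Total |
|---|---|---|---|
| 1.673 | 0.418 | 131.5 | 264 |
| 1.637 | 0.41 | 133.7 | 268 |
| 1.637 | 0.409 | 134.4 | 270 |
| 1.673 | 0.41 | 137.1 | 276 |

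Putting the control variance in both arms gives 302 to 314. Plain Poisson at the stated level does not give 334. Two unstated inputs would:
- **Extra variance.** With 167 per arm, the common variance is 167d²/(2k), which is 1.788 at d = 0.41 and 1.859 at d = 0.418. That is about 1.2 to 1.3 times the mean.
- **A stricter alpha.** At two-sided 2.5%, k = 9.505. With 1.673 and 0.41, n = 166.01 per arm, rounded up to 167, which is 334 in total.

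The later step does reproduce: 334/0.95 = 351.6, giving 352.

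**3. Effect on the test.** Let φ be the residual variance divided by the mean. It is assumed, because the documents give no value. Actual two-sided error = 2[1 − Φ(1.960/√φ)]. The unadjusted interval has 1/√φ of the correct width.

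| Assumed φ | Actual error | Interval too narrow by | Corrected interval wider by |
|---|---|---|---|
| 1.00 | 5.0% | 0% | 0% |
| 1.10 | 6.2% | 5% | 5% |
| 1.25 | 8.0% | 11% | 12% |
| 1.50 | 11.0% | 18% | 22% |

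A negative binomial simulation with no arm effect (171 per arm, 40,000 replicates) gave plain-Poisson error of 4.9%, 7.8% and 11.0% at φ = 1, 1.25 and 1.5. With a robust variance the error stayed between 4.9% and 5.3%.

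**4. Power with a variance that respects φ.** Evaluable patients: 360 × 0.95 = 342, or 171 per arm. Power = Φ(d/√[φ(m₀ + m₁)/171] − 1.960), over the input pairs in step 2 and the equivalent log-rate form:
- φ = 1: about 88–89%
- φ = 1.25: about 80–82%
- φ = 1.5: about 72–74%

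**The case against.** The strongest reply is that nothing in the documents shows over-dispersion. The heterogeneity they describe concerns function, mobility, comorbidity and frailty, not rehospitalization rates, and every error rate above rests on an assumed φ. Section 14.1 is also silent on how the variance will be estimated; it does not rule out a robust one. All of this stands. It limits the point to a gap in specification.

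Two stronger readings are tempting, and the documents support neither.

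- **That the pilot already shows over-dispersion.** If the pilot means are raw, the ± values cannot be standard deviations: whole-number counts with means 1.673 and 1.157 have standard deviations of at least √(0.673 × 0.327) = 0.469 and √(0.157 × 0.843) = 0.364. Read as standard errors, they imply variance above the mean once the arms exceed 1.673/0.392² = 10.9 and 1.157/0.349² = 9.5 patients. But this assumes that ± is a standard error, that the figures are unadjusted, and that the arms were that large. At 11 and 10 patients the ratios are 1.01 and 1.05, practically Poisson. The only clue to pilot size is indirect: Section 7.2.3 reports that "40% of participants were initially at level 1 for most domains, 33% were at level 2, and 27% were at level 3", which needs at least 15 patients but does not say whether they were the whole pilot or one arm.

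- **That 334 is wrong or too small, or that it proves over-dispersion.** It exceeds every plain-Poisson figure at the stated level. Because two-sided 2.5% reproduces it without extra variance, a dispersion of 1.25 is only a back-solved illustration.

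The scale of the issue is also fairly contested: this is a secondary outcome, and at mild dispersion the excess error is a few points or less. That limits how much the gap matters but gives no reason to leave it, given how little the remedy costs.

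**Conclusion.** The point holds as a gap in pre-specification that should be fixed. The plan's only secondary outcome is analysed by a model that forces variance to equal the mean, with no scale parameter, robust variance, alternative model or dispersion check stated anywhere. If residual dispersion were 1.10 to 1.5, the 5% test would run at about 6.2% to 11.0%. That range is an assumption, as is the application of the 5% level to this outcome.

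Separately, the printed pilot inputs disagree with each other, and 334 cannot be verified from what is stated. The discrepancies alone change the required size little (264 to 276). The claim of more than 80% power holds under plain Poisson, is borderline at dispersion 1.25, and fails at 1.5.

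Over-dispersion is not demonstrated, 334 is not shown to be too small, and the primary SPPB analysis of covariance is untouched.

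**What to change.** 1. **Section 14.1.** Name one method: the same Poisson model and covariates, with a robust (sandwich) variance for the test and the interval. Apply it to total rehospitalizations and to the exploratory event counts. Naming a single method matters, since a list of options would leave the choice open until the data are seen. State there that the two-sided 5% level covers the secondary test.

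2. **Section 14.2.** Correct or explain 1.673, 29.3% and 0.41, saying whether 29.3% is an adjusted estimate. State what ± denotes, the pilot size per arm, and the variance and alpha behind 334. Restate secondary power for 360 randomized (342 evaluable) under the robust method, with the range from step 4 of the working.

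The cost is wording only, with no change to recruitment or data collection. The downside is an interval about 5% wider at dispersion 1.10 and 12% wider at 1.25, where power is close to 80%. If the counts are truly Poisson, almost nothing is lost: in a simulation with the planned covariates (8,000 replicates), error was 5.4% with the robust variance and 5.1% without it.

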2.2 Secondary Objective

To systematically collect clinical outcomes data during the 6 months following the index hospitalization to test the following secondary hypothesis: The REHAB-HF intervention will reduce the 6-month all-cause rehospitalization rate.

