2.3 Other Objectives

- 1. To assess the economic impact of the intervention by comparing medical costs between treatment arms, inclusive of the cost for rehabilitation therapy, relative to its associated changes in health outcomes.
- 2. To estimate the proportion of the reduction in rehospitalizations explained by the intervention's effect on the SPPB score.
- 3. To examine the effect of the intervention on these exploratory endpoints:

- 1. Change in the Kansas City Cardiomyopathy Questionnaire (KCCQ) total score and physical component score at 3 months
- 2. Change in 6-minute walk distance (6MWD) at 3 months
- 3. Change in component scores of the SPPB at 3 months
- 4. Change in the 12-item short form health survey (SF-12), depression, and cognition measures at 3 months
- 5. Change in frailty status at 3 months
- 6. All-cause rehospitalizations at 1 month and 3 months
- 7. All-cause rehospitalizations 6 months from the date of randomization
- 8. All-cause combined rehospitalization and death at 6 months
- 9. Global rank endpoint of SPPB score + all-cause rehospitalization + death
- 10. Heart failure (HF)-specific rehospitalizations
- 11. Cardiovascular events
- 12. All-cause rehospitalization days
- 13. Total hospitalization days post-randomization
- 14. Total facility-free days alive
- 15. Deaths
- 16. Falls
- 17. Change in biomarkers at 3 months
- 18. Blood-based bioenergetics profiling.

3. Background

ADHF is the leading cause of hospitalization in persons > 60 years in the United States. Hospitalized ADHF is associated with severely reduced health-related quality of life (QOL), persistently high rehospitalization rates,(1) markedly increased mortality, and costs over \$39 billion per year.(2) Current HF management guidelines, even when perfectly adhered to, have had only modest impact on ADHF outcomes, particularly rehospitalizations in the older population.(1;3-5) Furthermore, several recent trials of new interventions to improve ADHF outcomes, such as telemonitoring,(6;7) alternative diuretic regimens,(8-11) novel agents(11;12) and biomarker guidance have been negative.(9;13) This suggests outcomes in older ADHF patients may be driven partly by mechanisms that are not addressed by current approaches.

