12.2 Secondary Efficacy Parameter

The secondary outcome for assessing the efficacy of the REHAB-HF intervention will be the total number of all-cause rehospitalizations during the 6 months following discharge from the index hospitalization.

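### The secondary rehospitalization count is modelled with no term for time at risk, and no rule says how deaths or incomplete follow-up enter the model

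*Combined protocol and SAP*

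**What the plan says.** Section 2.2 states the secondary hypothesis: "The REHAB-HF intervention will reduce the 6-month all-cause rehospitalization rate". Section 12.2 defines the outcome as "the total number of all-cause rehospitalizations during the 6 months following discharge from the index hospitalization".

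Section 14.1 gives the analysis: "the effect of the intervention on total all-cause rehospitalizations will be estimated using a Poisson model for modeling count data". The model compares the two arms and adjusts for site, age, gender and preserved or reduced ejection fraction; those are its only terms. A supplemental analysis is described as "adding the duration of the index hospitalization and the number of inpatient intervention sessions as additional covariates". Neither addition measures time at risk after discharge.

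Section 14.2 sizes the trial for "80% power to detect a 25% reduction (0.41 absolute difference) in the total number of all-cause rehospitalizations". It allows up to 5% of participants to be inevaluable for this outcome and does not say whether deaths are among them.

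On mortality, Section 3 lists "markedly increased mortality" among the consequences of hospitalized ADHF and gives no figure. Section 10.6 collects events up to 6 months after discharge, and Section 10.6.2 includes deaths. Section 12.3 has four exploratory endpoints that involve death: rehospitalization or death, a global rank, facility-free days alive, and deaths. No section gives an offset, an exposure time, or a rule for death or partial follow-up in the secondary model.

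**The concern.** A count model without exposure treats every participant as observed for the same length of time. Someone who dies in week 2 with no readmission would contribute a zero, exactly like someone followed for 6 months with none. If one arm loses more time to death or loss to follow-up, its count falls for that reason alone and looks like benefit. If the intervention prolongs survival, its arm has more time in which to be readmitted, and some real benefit is hidden. Section 1 hopes for better clinical outcomes, so equal survival cannot be taken for granted.

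This is the trial's only secondary outcome and the one that set its size (352 randomized, against 304 for the primary). The analysis of how much of the effect SPPB explains uses the same count, and Section 14.1 carries similar methods over to the exploratory endpoints. A correction for over-dispersion would change the standard error but not this shift in the estimate.

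**Working it through.** **The plan's own figures.** The inflation step reproduces: 334/0.95 = 351.6, so 352. The 334 does not follow from a pure Poisson variance. With (1.96 + 0.842)² = 7.849 and the printed control mean 1.673, a 25% reduction gives 7.849 × (1.673 + 1.255)/0.418² = 131.4, so 132 per arm and 264 in total (276 with the printed difference of 0.41). That is a separate matter. Neither figure involves time at risk, so the present point does not depend on them.

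**Expected shift.** Let q be 6-month mortality in an arm and f the average fraction of the window lived by those who die. With a constant event rate:

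- mean fraction of the window at risk = 1 − q(1 − f)
- expected raw-count ratio = true rate ratio × (fraction at risk, intervention ÷ control)

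All values of q and f are assumptions.

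| Deaths, control / intervention | True ratio | f = 0.5 | f = 0.25 |
|---|---|---|---|
| 10% / 10% | 1.00 | 1.000 | 1.000 |
| 10% / 15% | 1.00 | 0.925/0.950 = 0.974 | 0.8875/0.925 = 0.959 |
| 15% / 10% | 1.00 | 0.950/0.925 = 1.027 | 0.925/0.8875 = 1.042 |
| 8% / 16% | 1.00 | 0.920/0.960 = 0.958 | 0.880/0.940 = 0.936 |
| 15% / 10% | 0.75 | 0.75 × 1.027 = 0.770 | 0.75 × 1.042 = 0.782 |

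A constant death hazard agrees. Mean time at risk is then q/(−ln(1 − q)), which is 0.949 for 10% and 0.923 for 15%, a ratio of 0.972.

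**Against the trial's precision.** 80% power at a ratio of 0.75 implies a standard error of the log ratio of about 0.288/2.80 = 0.103. Ratios of 0.974 and 0.959 are shifts of 0.0267 and 0.0414 on the log scale, or 0.26 and 0.40 standard errors.

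**Simulation.** The settings were 180 per arm, gamma frailty variance 0.2, robust variance and a control mean of 1.637. That mean is the value that reproduces the plan's stated 29.3% (1 − 1.157/1.637) and 0.41 (0.25 × 1.637 = 0.409). Deaths were uniform over 6 months (spread) or over the first 2 months (early).

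| Deaths, control / intervention | Timing | True ratio | Raw count: ratio, rejection | Offset: ratio, rejection |
|---|---|---|---|---|
| 10% / 10% | spread | 1.00 | 1.000, 5.3% | 1.000, 5.7% |
| 10% / 15% | spread | 1.00 | 0.976, 5.5% | 1.002, 5.1% |
| 10% / 15% | early | 1.00 | 0.954, 7.6% | 1.000, 5.6% |
| 10% / 20% | spread | 1.00 | 0.950, 8.0% | 1.003, 5.1% |
| 10% / 20% | early | 1.00 | 0.909, 15.1% | 1.000, 6.3% |
| 15% / 10% | spread | 0.75 | 0.771, 68.4% | 0.751, 79.0% |

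The offset recovers the true ratio here because the simulated event rate is constant and unrelated to death.

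**When the event rate is not constant.** Suppose two-thirds of readmissions fall in the first half of the window and deaths occur at the midpoint, at 10% and 15%. The raw ratio is (1 − 0.15/3)/(1 − 0.10/3) = 0.950/0.967 = 0.983. With the offset it is (0.950/0.925)/(0.967/0.950) = 1.009. The offset then over-corrects slightly, but it stays closer to 1 than the raw count.

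**The case against.** Several counter-arguments have force.

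- A reader might infer that the objective (a rate) contradicts the endpoint (a number). The documents do not support that. Over a fixed window a mean count per patient can be called a rate, and Section 14.2 itself compares an event rate from a confirmatory sample with the pilot control arm's mean count.
- A reader might also infer that the plan deliberately scores early death as staying out of hospital. It does not say so; it is silent. Deaths might instead be meant to fall under the 5% inevaluable, although dropping them would select on an event after randomization.
- Total admissions over a fixed period, with death ending accrual, is a legitimate quantity. It suits the cost-offset question in Section 11.6.
- Every mortality figure above is assumed. Section 5.2 excludes several high-risk groups, and the pilot could evaluate 6-month hospitalizations in all participants. Bias needs unequal time at risk. With a 5-point gap spread over the window, the simulated error rate is close to nominal.
- The exploratory endpoints and the DSMB's review of deaths would make a mortality imbalance visible.

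These points limit the size and certainty of the concern. They do not supply the missing rule. The exploratory endpoints let a reader cross-check the secondary estimate but leave it unchanged, and if the fixed-window count is the intended estimand, the plan should say so and say how deaths enter it.

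**Conclusion.** The point holds as a gap in specification with a modest, conditional effect. The secondary model has no exposure term, and no section states how death or incomplete follow-up is handled. Under an assumed 5-point difference in 6-month mortality (10% against 15%), the ratio shifts by about 3–4%, in either direction. The shift is larger with wider gaps or earlier deaths and zero if time at risk is equal. Clear inflation of the error rate appeared only with early deaths or a 10-point gap. In the opposite case, where the intervention also reduces deaths (15% against 10%, spread), simulated power fell to 68% with the raw count, against 79% with the offset.

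The documents do not support a claim that the result will be biased, or biased towards the intervention. They give no mortality by arm, and the sign depends on which arm loses more time. The figures rest on assumed death rates and timing, a constant event rate, and no link between a participant's readmission risk and death.

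**What to change.** In Section 14.1, fit the count model with log(days alive and under follow-up from index discharge to 6 months) as an offset. Keep every participant with partial follow-up. Define the end of exposure as the earliest of death, last contact and 6 months. State what happens to anyone who dies before index discharge, since zero exposure has no logarithm. Report the raw-count model as a sensitivity analysis, beside deaths by arm and the planned rehospitalization-or-death endpoint. Align Section 12.2 with this wording, and settle it before any unblinded look at the outcome.

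The cost is a few lines of text. Deaths are already captured. No section names a last-contact date, so it must be derived from the visits and calls scheduled in Sections 7.1 and 9.1. The estimand becomes a while-alive rate ratio, which assumes a roughly constant event rate and does not remove informative death. That is why the raw count and the endpoint that includes death should stand next to it.
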